#### 6.4. Subset Analyses

No subset analyses are planned.

## **6.5. Baseline and Other Summaries and Analyses**

### **6.5.1. Baseline Summaries**

A breakdown of all participants will be provided by demographic characteristics (age, race, weight, body mass index, and height), extent of disease and prior use of conventional therapy in accordance with Pfizer data standards. Mean steroid use and duration of disease will also be presented by cohort. Baseline CDASI (activity and damage) will be summarized descriptively.

### **6.5.2. Study Conduct and Participant Disposition**

Participant evaluation groups will show end of study participant disposition and will show which participants were analyzed in the full analysis set, skin analysis set, and muscle analysis set, and as well as for safety, PK and PD. Frequency counts will be supplied for participant discontinuations by treatment. Disposition will also be summarized separately for participants who discontinue.

Data will be reported in accordance with reporting standards.

### **6.5.3. Study Treatment Exposure**

The number of the doses of active treatment will be recorded and summarized by cohort.

### **6.5.4. Concomitant Medications and Nondrug Treatments**

All concomitant medication(s) as well as non-drug treatment(s) will be provided in the listings. These will be listed for each cohort and cohort will be indicated. A separate listing may be provided for DM-related prior and concomitant medications.

## **6.6. Safety Summaries and Analyses**

The safety will be monitored over the study period that includes treatment and follow-up periods in all cohorts.

### **6.6.1. Adverse Events**

Overall standard AE endpoints for this study are incidence of TEAE, incidence of SAEs, and incidence of AEs leading to discontinuation. Separate AE tables will show the AE data for each cohort.

### **6.6.2. Laboratory Data**

Laboratory data will be listed and summarized by treatment in accordance with the sponsor reporting standards. The laboratory data listing will indicate cohort.

### 6.6.3. Vital Signs

Systolic blood pressure, diastolic blood pressure and pulse rate will be listed and tabulated by week with descriptive statistics (N, mean, standard deviation, median, minimum and maximum). Change from baseline (defined as mean pre-dose value collected at baseline) will also be summarized using the same descriptive statistics by week.

### 6.6.4. Electrocardiograms

Single 12-lead ECGs should be collected at times specified in the Schedule of Activities.

The following ECG data will be listed: QT, QTc (Fridericia's), heart rate, QRS duration, PR interval. QTc based on Fridericia's correction will be derived.

Baseline and change from baseline for QT, QTcF, heart rate, QRS, PR will be summarized using descriptive statistics by study week in each cohort. For QTcF a classification of absolute values and increase from baseline will be used.

The numbers of subjects with ECG outcomes within the specified categories (see [Section 9.4](#)) and number of participants with uncorrected QT values  $\geq 500$  ms will be summarized by treatment and study week.

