3. OBJECTIVES, ENDPOINTS, AND ESTIMANDS

Objectives	Endpoints	Estimands
Primary: 
To evaluate the long-term safety and tolerability of PF-06823859.	Primary: 
Incidence of AEs, laboratory abnormalities, changes in vital signs, and ECG findings.	Primary: 
There are no defined estimands for safety and tolerability endpoints; these will be analyzed using Pfizer data standards, as applicable.
Secondary: 
To evaluate the long-term efficacy of PF-06823859 in adult participants with moderate to severe DM.	Secondary: 
Change from baseline in CDASI activity score at Week 52.Absolute values and change from baseline of CDASI activity and CDASI damage scores at all scheduled timepoints.TIS score at Week 52 and at intermediate scheduled timepoints for participants who	Secondary: 
E1: This estimand uses a hypothetical estimand strategy (ICH E9 addendum) estimating the mean effect of PF-06823859 in the absence of intercurrent events (study withdrawal). This is the mean change from baseline to Week 52 CDASI activity score for all randomized and dosed participants with non-missing baseline score in the (a) Skin Analysis Set and (b) Muscle Analysis Set (see details in Section 9.1.1).These additional CDASI endpoints will be analyzed using E1 at all scheduled timepoints.E2: This estimand uses a hypothetical estimand strategy (ICH E9 addendum) estimating the mean effect of PF-06823859 in the absence of intercurrent events (study

	
entered from Stage 3 of Protocol C0251002.
 
Change from baseline in the CSMs of the TIS including PhGA, PtGA, MMT-8, HAQ-DI, muscle enzymes, and MDAAT at Week 52 and at intermediate scheduled timepoints.	
withdrawal). This is the mean TIS at Week 52 for all randomized and dosed participants included with non-missing baseline score in the Muscle Analysis Set (see details in Section 9.1.1).
 
The endpoints for the CSM of the TIS will be analyzed using E2 at Week 52 and all intermediate scheduled timepoints.
Tertiary/Exploratory:	Tertiary/Exploratory:	Tertiary/Exploratory:

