9.1. Statistical Hypotheses

No statistical hypothesis testing is planned for this study.

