9.3.5.2. Electrocardiogram Analyses

Changes from baseline for the ECG parameters QT interval, heart rate, QTc interval, PR interval, and QRS complex will be summarized by treatment and time. The Day 1 pre-dose ECG measurements will be used as a participant's baseline.

The number (%) of participants with maximum postdose QTc values and maximum increases from baseline in the following categories will be tabulated by treatment:

Safety QTc Assessment

Degree of Prolongation	Mild (msec)	Moderate (msec)	Severe (msec)
Absolute value	>450-480	>480-500	>500
Increase from baseline		30-60	>60

In addition, the number of participants with absolute QTc values ≥ 500 msec will be listed.

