9.5. Sample Size Determination

The sample size will be determined by the number of patients who enroll from Protocol C0251002 and any other future qualifying studies. It is anticipated that up to approximately 30 participants from Amended Stage 2 and Stage 3 of Protocol C0251002 will be enrolled to receive open-label study intervention.

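### SAP 6.6.4 does not clearly specify the protocol's per-participant table of maximum postdose QTc and maximum increase, and its bands and 500 ms flag differ from Protocol 9.3.5.2

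*SAP*

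**What the plan says.** The primary endpoint in Protocol Section 3 is "Incidence of AEs, laboratory abnormalities, changes in vital signs, and ECG findings". SAP 3.1.4 sends the reporting of ECG findings to SAP 6.6.4, so that section is where this part of the endpoint is specified.

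Protocol 9.3.5.2 states: "The number (%) of participants with maximum postdose QTc values and maximum increases from baseline in the following categories will be tabulated by treatment". Its absolute bands are >450-480, >480-500 and >500 ms. Its increase bands are 30-60 and >60 ms. It adds a listing for "the number of participants with absolute QTc values" of 500 ms or more.

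SAP 6.6.4 says that the counts in the SAP 9.4 categories, and the "number of participants with uncorrected QT values" of 500 ms or more, "will be summarized by treatment and study week". SAP 9.4 labels each QTcF band as a maximum and prints the absolute bands with strict inequalities at both ends: above 450 and below 480, above 480 and below 500, and above 500. The increase bands are 30 to below 60, and 60 or more. SAP 6.6.4 also lists QTcF, and SAP 9.4 lists in the study report any measurement that meets its criteria.

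**The concern.** The protocol's table answers a simple question: how many participants ever reached a given degree of prolongation. A by-week table answers a different one: how many were in a band at a given visit. If only the second is programmed, the reader of the report cannot recover the first from it.

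Two smaller mismatches sit beside this. A value exactly on 480 or 500 ms has no absolute band in the SAP, and the 500 ms flag is applied to QT where Protocol 9.3.5.2 applies it to QTc. The SAP explains none of these differences. With up to about 30 participants and only descriptive reporting, each prolongation is read individually, so it should be clear which table shows it.

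**Working it through.** No test or sample-size figure is involved (Protocol 9.1: "No statistical hypothesis testing is planned for this study"). The check compares the two sets of rules.

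**1. Bands.** Every whole-millisecond QTc from 440 to 559 and every increase from 0 to 119 was classified under both documents. They differ at three values only.

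| Value | Protocol 9.3.5.2 | SAP 9.4 |
|---|---|---|
| QTc 480 ms | first band (>450-480) | no band |
| QTc 500 ms | second band (>480-500) | no band |
| Increase 60 ms | lower band (30-60) | upper band (60 or more) |

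The strict signs are unlikely to be a reading error, because inclusive signs survive in the next row of the same SAP table.

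**2. Do the boundary values vanish?** Protocol exclusion 5 gives QTcF above 450 ms as an example of an excluding baseline finding, with a three-reading average deciding. From a baseline of 450 or less, 480 is a rise of at least 480 − 450 = 30 ms, and 500 is a rise of at least 500 − 450 = 50 ms. Both then fall in a SAP increase band and meet a listing criterion. The exception is a participant whose analysed baseline reading is above 450 although the average qualified. For example, from 455 a value of 480 is a rise of 25 ms and meets no SAP criterion. A value of 500 escapes only if the baseline reading is above 470 (500 − 30).

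**3. QT against QTcF at 500 ms.** QTcF = QT / (60/HR)^(1/3).

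| Heart rate (bpm) | QTcF when QT = 500 | QT when QTcF = 500 |
|---|---|---|
| 50 | 470.5 | 531.3 |
| 60 | 500.0 | 500.0 |
| 70 | 526.4 | 475.0 |
| 80 | 550.3 | 454.3 |
| 90 | 572.4 | 436.8 |

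The two flags agree only at 60 bpm. At 80 bpm a QTcF of 500 goes with a QT of about 454, which the QT flag does not pick up. At 50 bpm a QT of 500 is flagged although QTcF is about 471. The SAP still has a QTcF band above 500, however. Taking that band and the flag together, the QTcF value that loses its place is exactly 500.

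**4. Weekly counts against participants.** Assume 30 participants, four postdose ECG visits, and a 5% chance per visit of being in a given band. These rates are illustrative and not from the documents. The expected weekly count is 30 × 0.05 = 1.5. The expected number of participants ever in the band is 1.5 if it is always the same people, and 30 × (1 − 0.95^4) = 5.6 if visits are independent. The same weekly figures fit both.

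**5. ECGs without a study week.** SAP 9.1 windows are 7 days wide and 28 days apart, so 28 − 7 = 21 days in each cycle belong to no window (for example Days 89-109, between Weeks 12 and 16). An unscheduled ECG on those days has no study week under the stated rule. A repeat within a window does have one, but which reading represents the visit is settled by consultation, not by taking the largest.

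**The case against.** A reader might infer that the protocol's maximum-QTc table will not be produced at all. The documents do not support that. SAP 9.4 labels its bands as maxima, SAP 6.1.1 summarises categorical outcomes by participant counts and percentages, and the listed QTcF values would allow the table to be derived. What stands is that SAP 9.4 (maximum) and SAP 6.6.4 (study week) are not reconciled, and that no sentence in the SAP asks for a maximum across visits.

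A reader might also infer that boundary or unscheduled prolongations would be hidden. Steps 2 and 3 show that this is mostly not so. SAP 6.6.4 lists ECG data, a QTcF above 480 ms may also qualify as an adverse event under Protocol Appendix 7, and SAP 9.1 allows the visit-assignment rules to be adjusted after actual visit days are seen.

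The uncorrected QT count has its own rationale: Protocol 8.2.5 uses an absolute QT of 500 ms or more among its monitoring triggers. This stands, and it is a reason to keep the count and add the QTcF one.

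On the 60 ms boundary, the protocol itself varies: 8.2.5 and Appendix 7 include 60 in the higher side, while 9.3.5.2 and Appendix 10 do not. The SAP is therefore not a clean departure from a single protocol rule.

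Finally, both documents let the SAP modify the protocol's plans, with an amendment required only for major modifications to the primary endpoint. Nothing here clearly reaches that threshold.

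**Conclusion.** The point holds as a specification gap with a small effect. SAP 6.6.4 and 9.4 together do not clearly call for the protocol's once-per-participant table. Two absolute QTcF values (480 and 500 ms) have no band, one increase (60 ms) is placed differently, and the 500 ms flag uses QT where Protocol 9.3.5.2 uses QTc. Few of the roughly 30 participants are likely to be affected, no inference depends on the table, and the underlying values are listed. It still merits correction, because the table belongs to a primary safety endpoint and the repair is nearly free.

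This rests on three assumptions: the strict inequalities are as printed, baseline QTcF is mostly 450 ms or less as exclusion 5 implies, and the by-week wording in SAP 6.6.4 is meant literally.

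**What to change.** - **SAP 6.6.4:** add one table, overall and by cohort, that counts each participant once by maximum postdose QTcF and once by maximum increase, over all scheduled, repeat and unscheduled postdose ECGs. Keep the by-week summary.
- **SAP 9.4:** set the absolute bands to >450 to ≤480, >480 to ≤500, and >500 ms.
- **500 ms flag:** add a count and listing of participants with QTcF of 500 ms or more, and keep the uncorrected QT count as an addition.
- **60 ms increase:** for the analysis categories only, reconcile Protocol 9.3.5.2 and SAP 9.4 so that both place it in the same band. This does not touch the clinical triggers elsewhere in the protocol.

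The cost is a few lines of SAP text and one table shell, plus a small wording change in Protocol 9.3.5.2 if the SAP's side of 60 ms is kept. No new data are needed and no planned summary is lost.

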### 6.6.5. Physical Examination

All physical exam data will be provided in the listings.

## 7. INTERIM ANALYSES

*No formal interim analysis will be conducted for this study. As this is an open-label study, the sponsor may conduct unblinded reviews of the data during the course of the study for the purpose of safety assessments, facilitating PK/PD modeling, and/or supporting clinical development.*

## 9. APPENDICES

### 9.1. Definition and Use of Visit Windows in Reporting

The currently assumed assignment of the observations to visits is based on the participant's arrival day. It assumes that the arrival times for postbaseline visits occur within the (-3,3) days time window centered around the target day as specified in the schedule of activities. We will check the validity of the assumption by the analysis of distributions of actually observed arrival days at the end of the study and may update the assignment rules slightly.

Visit Label	Targeted Day	Analysis window
Baseline*	Day 1 (reference day)	Day 1 (reference day)
Week 4	Day 29	Days 26-32
Week 8	Day 57	Days 54-60
Week 12	Day 85	Days 82-88
Week 16	Day 113	Days 110-116
Week 20	Day 141	Days 138-144
Week 24	Day 169	Days 166-172
Week 28	Day 197	Days 194-200
Week 32	Day 225	Days 222-228
Week 36	Day 253	Days 250-256
Week 40	Day 281	Days 278-284
Week 44	Day 309	Days 306-312
Week 48	Day 337	Days 334-340
Week 52	Day 365	Days 362-368
Week 56	Day 393	Days 390-396
Week 60	Day 421	Days 418-424
Week 64	Day 449	Days 446-452
Week 68	Day 477	Days 474-480

\*Baseline occurs within 7 days of Week 24 C0251002 Day 1.

If more than one observation from the same participant falls into the same window then the association of the observation with the visit will be done after the consultation with the study clinician and lead statistician.

## 9.2. CDASI

**Figure 2. Presents the CDASI Scale**

COPYRIGHTED MATERIAL

The main outcomes of interest are the activity score and damage score.

PFIZER GENERAL BUSINESS  
TMF Doc ID: 98.03

The official version of this form is located in the electronic document management system.

DMB02-GSOP-RF02 6.0 *Statistical Analysis Plan Template* 01-Jul-2021

### 9.2.1. The Activity Score (AS)

The Activity Score (AS) is calculated as a sum of the contribution from the extent score (ES), Gottorn hands score (GHS), peringual score (PS) and alopecia score (AS).

$$AS = ES + GHS + PS + AS$$

The total extent score (ES) is obtained by summing up scores for the total erythema (ER, quantifies redness of the skin or mucous membranes), total scaling (SC, quantifies peeling of the skin) and total erosion/ulceration (EU, quantifies presence of the deeper wound).

$$ES = ER + SC + EU$$

Total erythema (ER), scaling (SC) and erosion/ulceration (EU) scores are calculated as a sum of the contributions from 15 individual areas of the body. The range of the total erytherma score is 0-45, the range of the total scaling score is 0-30 and the range of total erosion/ulceration is 0-15. The resulting range of the extent score is 0-90.

Gottorn hands score (GHS) characterizes papules (swellings) on hand and is a sum of the papule's characterization score (range 0-6) and ulceration score (range = 0-1).

Peringual score (PS) characterizes abnormalities around nails and its range is 0-2. The alopecia score (AS) characterizes hair loss and has the range 0-1.

The resulting range of the activity score is 0-100.

### 9.2.2. Damage Score

The Damage Score (DS) is calculated as a sum of the total poikiloderma score (POLS), total calcinosis score (CALS) and Gotorn's hands damage score (GHDS).

$$DS = POLS + CALS + GDHS$$

The polikiolderma score characterizes specific depigmentation in the particular area and calcinosis score characterizes calcification of the skin in the particular area. The total polikiolderma score (POLS) and the total calcinosis score (CALS) are summed up over 15 individual areas in the body and each of them has range 0-15. The Gotorn's hands damage score (GHDS) has the range 0-2 so that the damage score (DS) has the range 0-32.

In our analysis we will look at the activity score (AS), damage score (DS).

For the activity score we will analyze the following subscores: total extent score (ES), total erythema score (ER), total scaling (SC) and total erosion/ulceration scores (EU), Gottorn hands score (GHS), peringual score (PS), and alopecia score (AS).

For the damage score we will analyze the following subscores: total poikiloderma score (POLS), total calcinosis score (CALS) and Gotom's hands damage score (GHDS).

### 9.3. TIS using CSM in DM

The total improvement score is the sum of all 6 improvement scores associated with the change in each core set measure. A total improvement score of  $\geq 20$  represents minimal improvement, a score of  $\geq 40$  represents moderate improvement, and a score of  $\geq 60$  represents major improvement.

ACR/EULAR CRITERIA FOR CLINICAL RESPONSE IN ADULT DERMATOMYOSITIS AND POLYMYOSITIS

Table 3. Final myositis response criteria for minimal, moderate, and major improvement in adult dermatomyositis/polymyositis (DM/PM) and combined adult DM/PM and juvenile DM clinical trials and studies\*

**COPYRIGHTED MATERIAL**

#### 9.4. Categories for ECG and Vital Sign Outcomes

The following Pfizer's standard will be used. For the sitting measurements of pulse rate the categories for the supine pulse rate (min <40 bpm and max >120 bpm) will be used.

##### Categories for QTcF

QTcF (msec)	450 < max. < 480	480 < max. < 500	max. > 500
QTcF (msec) increase from baseline	30 ≤ max. < 60	max. ≥ 60	

##### Categories for PR and QRS

PR (msec)	max. ≥ 300	
PR (msec) increase from baseline	Baseline >200 and max. ≥25% increase	Baseline ≤100 and max. ≥50% increase
QRS (msec)	max. ≥ 200	
QRS (msec) increase from baseline	Baseline >100 and max. ≥25% increase	Baseline ≤100 and max. ≥50% increase

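### SAP 9.4: the two PR change-from-baseline categories omit baselines above 100 and up to 200 msec, so the categorical PR count misses large rises that stay below 300 msec

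*SAP*

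**What the plan says.** SAP 9.4 introduces its ECG and vital-sign categories with "The following Pfizer's standard will be used". For PR it gives three categories:

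- an absolute one, maximum PR ≥300 msec;
- a change category, "Baseline >200 and max. ≥25% increase";
- a second change category, "Baseline ≤100 and max. ≥50% increase".

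The QRS row has the same layout. Its first change cell is "Baseline >100 and max. ≥25% increase", and its second is word for word the second PR cell.

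SAP 6.6.4 puts these cells to use: "The numbers of subjects with ECG outcomes within the specified categories" are to be summarised by treatment and study week. The same section also covers PR in two other ways. Individual values appear under "The following ECG data will be listed", and "Baseline and change from baseline for QT, QTcF, heart rate, QRS, PR will be summarized" by study week in each cohort.

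For QTcF, the absolute bins in SAP 9.4 are strict on both sides (above 450 and below 480, above 480 and below 500, above 500), and the top increase category starts at ≥60 msec. SAP 6.6.4 adds the "number of participants with uncorrected QT values" of 500 ms or more. Protocol 9.3.5.2 has >450-480, >480-500 and >500 for the absolute value, 30-60 and >60 for the increase, and applies the 500 msec criterion to QTc. It defines no PR categories.

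**The concern.** Two change cells that apply different percentage thresholds above and below a baseline limit need to meet at one limit. The QRS cells meet at 100 msec. The PR cells do not: one starts above 200 and the other stops at 100. The shared second cell suggests that the QRS limit may have been carried into the PR row, although the documents do not confirm this.

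ECG findings belong to the primary endpoint, and SAP 9.4 is the only definition of the categorical PR analysis. A zero in the PR-change table, built as written, could not be read as absence of large PR rises among participants with a baseline in the omitted range. The ECG exclusion criterion in protocol 5.2 states no PR limit, so eligibility does not keep such baselines out of the study.

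**Working it through.** **Inputs (SAP 9.4).** With b the baseline PR and m the maximum PR, both in msec:

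- change cell 1: b > 200 and m ≥ 1.25b
- change cell 2: b ≤ 100 and m ≥ 1.5b
- absolute category: m ≥ 300
- QRS change cells, for comparison: b > 100 with ≥25%; b ≤ 100 with ≥50%

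**Step 1: uncovered baselines.** Neither b > 200 nor b ≤ 100 holds for 100 < b ≤ 200. In whole msec that is 101 to 200, or 100 values. For QRS, every baseline satisfies either b > 100 or b ≤ 100, so there are 0.

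**Step 2: rises of 50% or more in no PR category.** For an uncovered b, the only remaining category is m ≥ 300. A rise of at least 50% therefore escapes every PR category when 1.5b ≤ m ≤ 299. The last column counts the missed peaks that also lie at or below 280 msec, because protocol Appendix 7 names new PR prolongation above 280 msec as a possible AE.

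| b | 1.5b | Peaks in no PR category | Whole-msec values | Of these, ≤280 |
|---|---|---|---|---|
| 110 | 165 | 165-299 | 135 | 116 |
| 120 | 180 | 180-299 | 120 | 101 |
| 140 | 210 | 210-299 | 90 | 71 |
| 160 | 240 | 240-299 | 60 | 41 |
| 180 | 270 | 270-299 | 30 | 11 |
| 190 | 285 | 285-299 | 15 | 0 |
| 199 | 298.5 | 299 | 1 | 0 |
| 200 | 300 | none | 0 | 0 |

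At b = 200 a 50% rise reaches 300 and meets the absolute category, so complete escape applies to 100 < b < 200. The last baseline from which a 50% rise can stay at or below 280 is 186 (1.5 × 186 = 279; 1.5 × 187 = 280.5).

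**Step 3: rise needed before the absolute category responds, (300 − b)/b.** b = 120: 150%. b = 140: 114%. b = 160: 87.5%. b = 180: 66.7%. b = 190: 57.9%.

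**Step 4: what the rule counts.**

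- 100 to 150: 150/100 = 1.50 (+50%), counted.
- 101 to 299: 299/101 = 2.96 (+196%), not counted.
- 210 to 263: 263/210 = 1.252 (+25.2%), counted.
- 190 to 285: 285/190 = 1.50 (+50.0%), not counted.

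**Step 5: with the second cell read as b ≤ 200.** Every baseline then falls under exactly one change cell, and 140 to 210, 160 to 240, 180 to 270 and 190 to 285 are all counted.

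**Step 6: QTcF boundaries (minor).** Whole-msec values above 450 in no SAP absolute bin: 480 and 500. In the protocol 9.3.5.2 bins: none. An increase of exactly 60 msec is in the top category in the SAP (≥60) and in the 30-60 category in protocol 9.3.5.2. The protocol is itself divided on this boundary (≥60 in 8.2.5 and Appendix 7; >60 in 9.3.5.2 and Appendix 10) and on the 500 msec variable (QT in 8.2.5, QTc in 9.3.5.2). The SAP does not say which passage it follows.

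**The case against.** The strongest case against is one of importance. Protocol 9.3.5.2 asks for categorical tabulation of QTc only; for PR it asks for a summary of change from baseline, which SAP 6.6.4 provides along with a listing. The PR categories are the SAP's own addition, the study is open-label with about 30 participants and no hypothesis test, and no decision rule uses the count. The investigator's comparison with baseline, the >280 msec AE prompt and the documented ECG review all continue. This stands, and it limits the consequence to one categorical table. It does not make that table correct: weekly means do not count participants with a large rise, and a listing leaves the count to the reader.

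A second objection is that any rule with 25% and 50% thresholds will count some smaller changes from higher baselines. That is true in general; after the fix, 190 to 284 (+49.5%) would still not be counted. But 190 to 285 would be, so that example does show the gap. It is not an example of a rise that goes wholly unflagged, because 285 exceeds 280; 160 to 240 is.

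Third, the ≤200 limit appears nowhere in the documents and the sponsor standard is not available to us. This stands, so the cut-point is a suggestion to be confirmed.

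Fourth, the QTcF points touch only exact boundary values, and the protocol's different 60 msec rules serve different purposes. The SAP may also modify the planned analyses. These points are therefore minor and concern the SAP tabulation only.

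**Conclusion.** The concern holds. As written, the PR change categories in SAP 9.4 omit baselines above 100 and up to 200 msec, and for baselines above 100 and below 200 a rise of 50% or more that peaks under 300 msec is in no PR category.

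The effect is confined to the categorical PR-change count and to any outlier listing built on the same cells. The listing sentence in SAP 9.4 sits beneath the vital-signs table and does not say whether it covers ECG. The enumeration assumes whole-msec values and no distribution of PR. The number of participants affected cannot be estimated from the documents and may be zero. The table was read from PDF, but both cells are legible and nothing suggests a lost value.

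This should be corrected: the rule gives a wrong count within a primary-endpoint analysis, and the correction is small.

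**What to change.** - **PR row, SAP 9.4.** Make the two change cells complementary at one cut-point. The table's pattern suggests >200 and ≤200; confirm against the sponsor standard before editing.
- **QTcF absolute bins, SAP 9.4 (minor).** Close them so that 480 and 500 each fall in one bin, as in protocol 9.3.5.2.
- **60 msec increase (minor).** State one boundary for the SAP tabulation and the protocol passage it follows.
- **500 msec count, SAP 6.6.4 (minor).** Either report the number with QTcF ≥500 msec alongside uncorrected QT ≥500, or state that the SAP departs from protocol 9.3.5.2.

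The monitoring, AE and discontinuation thresholds in protocol 8.2.5, Appendix 7 and Appendix 10 are for the sponsor to reconcile; nothing here changes them.

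The cost is one PR cell after a check of the standard, the QTcF bin edits and one line in SAP 6.6.4. No data collection or visit changes.
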